13.2.2.7 VAS Assessment of Pain

The percentage change from baseline VAS pain score will be analyzed within treatment group and between treatment groups. An overall comparison among the 3 treatment groups will be performed using a one-way Analysis of Variance. Pairwise comparisons of the treatment groups will be made using t-test or non-parametric test as appropriate. While the primary assessment will be based on scores at Visit 12 (after 18 weeks of treatment), summaries will also be prepared for each of the other visits. If data are missing, a last observation carried forward procedure will be used, including the baseline, if necessary.

The VAS pain scores collected during the active treatment stage of the study (Stage 3) will also be summarized.

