8.1 Study Endpoints

Primary Endpoint

- Change and percent change in the individual BBSS scores of the three patient reported outcomes (dysmenorrhea, dyspareunia and non-menstrual pelvic pain) by study visit and treatment cycle

Secondary Endpoints

- Change in daily average use and percent change of prescription analgesics from the baseline menstrual cycle to the matching period leading up to Week 18, the last day of dosing of the first cycle of treatment.
- Change in daily average use and percent change of over the counter analgesics from the baseline menstrual cycle to the matching period leading up to Week 18, the last day of dosing of the first cycle of treatment, calculated based on days with reported values.
- Change in daily average use and percent change of overall medication use, prescription and over the counter, from the baseline menstrual cycle to the matching period leading up to Week 18, the last day of dosing of the first cycle of treatment, calculated based on days with reported values.
- Change and percent change in BBSS score incorporating the two physician-reported scores by study visit and treatment cycle.
- Change and percent change in the individual BBSS scores of the three patient reported outcomes (dysmenorrhea, dyspareunia and non-menstrual pelvic pain) by study visit and treatment cycle.
- Change from baseline in pain assessed using a Visual Analog Scale (VAS) by study visit and treatment cycle.
- Change from baseline in daily average dysmenorrhea and non-menstrual pelvic pain using an 11-point numerical rating scale (NRS) by study visit and treatment cycle.

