10. ASSESSMENT OF EFFICACY

10.1 Study Endpoints

Primary Endpoint

- Change and percent change in the individual BBSS scores of the three patient reported outcomes (dysmenorrhea, dyspareunia and non-menstrual pelvic pain) by study visit and treatment cycle.

Secondary Endpoints

- Change in daily average use and percent change of prescription medications from the baseline menstrual cycle to the matching period leading up to Week 18, the last day of dosing of the first cycle of treatment.
- Change in daily average use and percent change of over the counter medications from the baseline menstrual cycle to the matching period leading up to Week 18, the last day of dosing of the first cycle of treatment, calculated based on days with reported values.
- Change in daily average use and percent change of overall medication use, prescription and over the counter, from the baseline menstrual cycle to the matching period leading up to Week 18, the last day of dosing of the first cycle of treatment, calculated based on days with reported values.
- Change and percent change in BBSS score incorporating the two physician-reported scores by study visit and treatment cycle.
- Change from baseline in endometrial pain assessed using a Visual Analog Scale (VAS) by study visit and treatment cycle.
- Change from baseline in daily average dysmenorrhea and non-menstrual pelvic pain using an 11-point numerical rating scale (NRS) by study visit and treatment cycle.

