13.2.2.8 Assessment of Pain Using the NRS

The average daily assessment will be calculated separately for dysmenorrhea and pelvic pain within each key 28-day baseline and treatment period. The percentage change from baseline NRS pain score will be analyzed within treatment group and between treatment groups. An overall comparison among the 3 treatment groups will be performed using a one-way Analysis of Variance. Pairwise comparisons of the treatment groups will be made using t-test or non-parametric test as appropriate. While the primary assessment will be based on scores during the 28-day period prior to Visit 12 (after 18 weeks of treatment), summaries will also be prepared for each of the other visits.

The average daily assessment of dysmenorrhea and pelvic pain scores collected during the active treatment stage of the study (Stage 3) will also be summarized.

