6.7.7 VAS

VAS pain assessment scores and the percentage change from baseline will be summarized.

The statistical significance of the percentage change from baseline within treatment groups will be based on a paired t-test or Wilcoxon signed-rank test, as appropriate. The percentage change from baseline will be compared between groups using a t-test or Wilcoxon rank-sum test, as appropriate.

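### The VAS endpoint is defined as change from baseline, but both analysis sections test only percentage change, which costs power mainly in the within-arm tests

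*Protocol*

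**What the plan says.** Endpoint definition. Section 10.1 of the current protocol lists "Change from baseline in endometrial pain assessed using a Visual Analog Scale (VAS) by study visit and treatment cycle". Section 8.1 has "Change from baseline in pain assessed using a Visual Analog Scale (VAS) by study visit and treatment cycle", and the synopsis matches it. The same lists name both change and percent change for the BBSS items and the medication items, but only change for the VAS and the NRS.

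Protocol analysis. Section 13.2.2.7 says "The percentage change from baseline VAS pain score will be analyzed within treatment group and between treatment groups", then "An overall comparison among the 3 treatment groups will be performed using a one-way Analysis of Variance". Pairwise comparisons use a t-test or a non-parametric test as appropriate. Section 13.2.2.8 treats the NRS the same way: "The percentage change from baseline NRS pain score will be analyzed within treatment group and between treatment groups".

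SAP analysis. Section 6.7.7 says "VAS pain assessment scores and the percentage change from baseline will be summarized". Within arms, "The statistical significance of the percentage change from baseline within treatment groups will be based on a paired t-test or Wilcoxon signed-rank test, as appropriate". Between arms, "The percentage change from baseline will be compared between groups using a t-test or Wilcoxon rank-sum test, as appropriate". SAP 6.1 uses the Shapiro-Wilk test to decide when rank methods replace t-tests and ANOVA.

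Elsewhere the SAP tests change for daily endometriosis pain (6.7.4) and for BBSS scores (6.7.5, 6.7.6), and both forms for analgesic use (6.7.3). Among the visible sections, only the VAS is tested solely as a percentage.

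**The concern.** The defined endpoint and the tested variable are different quantities. A reader of the VAS result would not learn whether mean VAS change differs from zero or differs between arms.

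The substitution is not neutral. A fall cannot exceed 100%, while a rise from a low baseline has no comparable limit. A few women with low baselines can therefore dominate both the mean and the SD of the percentages. That pulls the within-arm mean upward, against the direction of benefit, and adds noise. The visible eligibility text sets a BBSS minimum but no VAS minimum. No visible rule covers a baseline VAS of 0, where the percentage is undefined.

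**Working it through.** **1. Is the stated endpoint tested anywhere?** Two general clauses might fill the gap. The synopsis says other continuous efficacy variables are handled like its ANCOVA example, but that example is itself a percentage change, and 13.2.2.7 specifies ANOVA for the VAS. SAP 6.1 permits further analyses but specifies none. Neither prespecifies a test of VAS change.

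**2. Why the mean percentage is off zero.** Let X be baseline and Y Week 18. The mean percentage change is 100 × (E[Y/X] − 1). If there is no true change and X and Y are interchangeable, E[Y/X] = E[X/Y]. Since Y/X + X/Y ≥ 2, it follows that E[Y/X] ≥ 1, with equality only if every score is unchanged. The mean of Y − X is 0.

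Example: one woman goes from 20 to 40 and another from 80 to 60.
- Mean change = (20 − 20)/2 = 0 points.
- Mean percentage change = (100 − 25)/2 = +37.5%.

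**3. Inputs.** From the documents: 20 per arm, two-sided 0.05, and the tests above. The visible power statement (18 per group, 80%) shows no effect size or SD and is not tied to the VAS, so it cannot be reproduced and does not bear on this point. Everything else is assumed: a 0–100 scale, baseline mean 40–60, SD 15–25, correlation 0.5–0.7, lowest baseline 1–10, and various true falls. There were 1,500 to 4,000 simulated trials per setting. At 1,500 the standard error is at most √(0.25/1500) = 1.3 points, and repeat runs of one setting agreed within about 4 points.

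**4. No true change.** Mean percentage change was +4.4% to +17.6% in one set of settings. In a second set it was about +30% (mean 50, SD 25, floor 5), about +10% (mean 60, SD 20) and +4% (mean 60, SD 15). Mean change was −0.9 to 0.0 points, and the median percentage change was close to 0.

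Rejection rates on percentages were 5–10% within arms and 3.4–5.3% between arms.

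**5. Within-arm power.** The switch is Shapiro-Wilk, then Wilcoxon signed-rank. The last three rows use a separate set of runs; correlation is 0.5 there and in the other SD 25 rows.

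| Assumed setting | Points | %, t-test | %, with switch |
|---|---|---|---|
| Mean 50, SD 25, 40% fall | 99% | 51% | 79% |
| Mean 50, SD 25, 20-point fall | 93% | 54% | 75% |
| Mean 50, SD 20, 20% fall | 66% | 27% | 39% |
| Mean 60, SD 20, 20% fall | 79% | – | 57% |
| Mean 60, SD 20, 40% fall | 100% | 91% | 99% |
| Mean 60, SD 15, 40% fall | 100% | 99% | – |
| Mean 50, SD 20, 10-point fall | 62.9% | 35.3% | 42.9% |
| Mean 50, SD 25, 10-point fall | 46.8% | 20.2% | 28.1% |
| Mean 50, SD 25, 30% fall | 90.7% | 45.4% | 63.8% |

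The switch recovers only part of the loss, because the signed-rank test still gives inflated rises larger ranks. The near-zero loss at mean 60, SD 15 is for a large effect, where both powers are close to 100%.

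**6. Between-arm power.** The switch here is to rank-sum.

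| Assumed setting | Points, t | %, t | Points, switch | %, switch |
|---|---|---|---|---|
| Mean 50, SD 25, 40% fall | 78% | 41% | 79% | 75% |
| Mean 50, SD 25, 20-point fall | 70% | 48% | 70% | 75% |
| Mean 60, SD 20, 40% fall | 98% | 87% | 98% | 98% |
| Mean 60, SD 20, r = 0.7, 20% fall | 71.7% | 57.5% | 71.5% | 66.5% |
| Mean 50, SD 20, 10-point fall | 33.9% | 28.9% | 33.6% | 34.1% |

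With the switch, the difference runs from a loss of about 5 points to a small gain.

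**The case against.** The strongest reply is that the randomised comparison is what shows a drug effect, and it is nearly unharmed. Protocol 13.2.2.7 and SAP 6.7.7 both allow a rank test pairwise, and SAP 6.1 supplies Kruskal-Wallis for the overall comparison. A plain t-test on badly skewed percentages is therefore not what is planned. This stands. A reader might infer from the mismatch that a real drug-placebo difference would be missed; the planned rule does not support that.

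A reader might also infer that an unchanged placebo arm would be reported as having worsened. The mean percentage would suggest it, but SAP 6.7.7 also summarises the scores and SAP 6.1 requires medians, both of which would show no shift.

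The largest losses depend on low baselines, which the documents do not establish. Entry requires a BBSS of at least 7, pain medication and symptoms over at least 3 cycles. In the +30% setting, the 5% of women with baseline 10 or below produce about two-thirds of the excess; without them it is +10.5%. This limits the size, not the direction.

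The endpoint wording may be loose rather than deliberate: 8.1 lists the BBSS patient scores as both primary and secondary, and SAP section 5 speaks only of changes in pain assessments. Intent cannot be settled from the text, but the sections still disagree.

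The NRS is less clear. SAP 6.7.4 tests change in daily endometriosis pain and may be the NRS analysis. SAP 6.7.1 and 6.7.2 are not visible.

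**Conclusion.** The mismatch holds in both documents: the VAS endpoint is change from baseline, and only percentage change is tested. The practical harm is a mean percentage biased upward by about 4 to 30 points under no true change, and lost within-arm power when baseline spread is wide or the effect modest.

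The documents do not support a claim of inflated type I error between arms or of material between-arm power loss under the planned rank-test rule. Only a t-test or ANOVA applied to the percentages regardless of skew loses materially. Within arms, the 5–10% null rejection makes lost power the main harm rather than a large false-positive excess.

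All magnitudes rest on assumed VAS distributions. For the within-arm tests, no setting tried favoured percentage change. Severity is low: this is one secondary endpoint in a phase 2 trial whose p-values, by Protocol 13.3, serve to quantify differences between groups.

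**What to change.** In Protocol 13.2.2.7 and SAP 6.7.7, make change from baseline in VAS points at Visit 12 the tested variable, within and between arms. Add it to the SAP 6.7.7 summaries and keep percentage change as a descriptive row. In Protocol 13.2.2.8, align the NRS analysis with its change-from-baseline endpoint, and with SAP 6.7.4 if that section covers the NRS.

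If percentage change is what the sponsor wants, the synopsis, 8.1 and 10.1 should say so, and a rule for a baseline of 0 should be added.

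The cost is a few words in each section, with no new data or patients. The one downside is that percentage change is no longer the tested VAS figure.

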13.2.2 Efficacy Analyses

Efficacy analyses will be conducted in the modified Intent-to-Treat population, which will consist of all subjects who are randomized, who receive study drug, and who have some post-baseline efficacy data.

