Subjects who complete at least 28 days after Visit 3 and wish to discontinue treatment due to lack of efficacy will be eligible to start active treatment (stage 3). Subjects who discontinue the study prior to this date will not be eligible for additional treatment.

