13.2.2 Efficacy Analyses

An analysis will be conducted once Stage 2, the first cycle of treatment, has been completed. A later analysis will focus on the data collected from the active treatment stage of the study, Stage 3.

Efficacy analyses of the first cycle of treatment will be conducted in the Intent-to-Treat population, which will consist of all subjects who are randomized and who receive study drug. Subjects with missing post-baseline data will have a value of “no change” imputed for analysis.

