13.3 General Statistical Issues

A Statistical Analysis Plan (SAP) will be developed prior to the analyses of the first cycle of treatment. Two analyses will be conducted. The first analysis will occur when all subjects have completed the first cycle of treatment (Week 18) and the second will be conducted once all subjects have completed the active treatment stage of the study (Stage 3).

Statistical significance will be declared if the two-sided p-value is ≤ 0.05 . Since the study was not powered for efficacy assessments based on statistical hypotheses, the p-values reported at the conclusion of the study are being reported to quantify the difference in the treatment effect between treatment groups.

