3. STUDY DESIGN

3.1 OVERVIEW AND LENGTH OF STUDY

ZPE-202 is a phase 2, 3-arm study with an 18 week active dosing period and an option to extend treatment for 2 additional cycles. The study will be conducted in three stages.

In the first stage, women will undergo a baseline assessment period with placebo or no study medication until their second ovulation event. Endometriosis pain, dysmenorrhea, non-

[REDACTED]

In the second stage (placebo-controlled), following the baseline assessment period, subjects will be randomized into one of 3 arms (placebo, 6 mg Proellex, 12 mg Proellex) in a 1-1-1 fashion. The start of the 18 week dosing period for the first cycle of treatment should commence as soon after ovulation as possible, after which subjects will be followed until menses returns. Subjects who do not wish to receive additional cycles of treatment after stage 2 will have their last visit scheduled after blood flow has stopped. During this off-drug interval subjects will continue to record study information in the daily diaries.

After completing a minimum of 28 days of treatment in the second stage of the study, subjects may discontinue the study and still be eligible to qualify for 2 additional treatment cycles.

In the third stage (active treatment), subjects who are eligible to receive additional cycles of treatment and who elect to continue treatment will be scheduled to start dosing in their next course 21 days (+/- 2 days) after the start of bleeding, following the first menses after the end of

their first course of treatment (off-drug interval). Subjects will receive 2 courses of additional active treatment separated by an off-drug interval (ODI), after which they will continue to record study information in the daily diary. Subjects randomized to placebo in the second stage will receive 12 mg of Proellex in this stage. Those randomized to Proellex in the second stage will retain their current dose level for the duration of this stage. The final follow-up visit will be scheduled after blood flow has stopped.

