6. STATISTICAL METHODOLOGY AND ANALYSES

6.1 GENERAL CONSIDERATIONS

Standard statistical methods will be employed to analyze all data. It is anticipated that the following techniques may be used: paired t-test; independent two-sample t-test; ANOVA; chi-square test; and Fisher's exact test. Assumptions of normality will be tested using the Shapiro-Wilk test. If distributional assumptions are violated, non-parametric techniques, such as the Wilcoxon signed-rank test, Wilcoxon rank-sum test, and Kruskal-Wallis test, will be employed. Summaries for quantitative variables will include the sample size, mean, median, standard deviation, minimum, and maximum. Summaries for categorical variables will include the number and percent of patients for each outcome. Statistical significance will be declared if the two-sided p-value is ≤ 0.05 . Additional statistical analyses, other than those described in this SAP, may be performed if deemed appropriate.

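### Carrying the last value forward to Week 18 for VAS, analgesic use and bleeding can enter a week-4 value as Week 18, because women may leave for lack of efficacy from day 28; the treatment difference can be biased either way

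*Protocol*

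**What the plan says.** In the latest protocol version shown, Section 13.2.2.7 (VAS) ends its analysis paragraph with "If data are missing, a last observation carried forward procedure will be used, including the baseline, if necessary". Sections 13.2.2.1 to 13.2.2.3 (prescription, over-the-counter and overall analgesic use) and 13.2.2.6 (bleeding) carry the same sentence. All set the main assessment at Visit 12, after 18 weeks. The VAS section adds that "summaries will also be prepared for each of the other visits", so scores from earlier visits exist.

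From day 28 after Visit 3, under Protocol 8.2.1, women who "wish to discontinue treatment due to lack of efficacy will be eligible to start active treatment (stage 3"). The synopsis gives the same 28-day exit without naming a reason, and SAP 3.1 says "subjects may discontinue the study and still be eligible to qualify for 2 additional treatment cycles". In Stage 3 every woman receives active drug.

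Protocol 13.2.2 has a general rule: "Subjects with missing post-baseline data will have a value of" no change imputed. SAP 1 (Introduction) confines the first analysis to Stage 1 and Stage 2 data. The visible SAP endpoint sections (6.7.3 to 6.7.7) name tests but no missing-data rule; Sections 6.7.1 and 6.7.2 are not in this copy.

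**The concern.** The plan creates an exit route, ties it to poor response and offers active drug to those who take it. Missing Week 18 values related to earlier outcome are therefore foreseeable. For a woman who uses this route at the first opportunity, the carried VAS score dates from about week 4. For analgesics it is the average over the first 28 days. Either would stand as a Week 18 result.

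Protocol 13.3 says "the p-values reported at the conclusion of the study are being reported to quantify the difference in the treatment effect between treatment groups". The size of the Week 18 difference is thus what these analyses are meant to deliver. Carrying forward can shrink or enlarge it, depending on how many leave each arm and on how each arm changes between week 4 and week 18.

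**Working it through.** **Time gap.** Week 18 is day 126. 28/126 = 22% of the dosing period, so a value may be carried over 18 - 4 = 14 weeks.

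**The plan's own figure.** Protocol 13.1 gives 18 per group for 80% power, but the effect size and SD are not visible. Inverting it (two-sided 0.05, normal approximation) gives a standardized difference of 0.934. The point does not depend on this; it only shows that a true difference of 0.90 SD is a reasonable scale for illustration.

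**Direction, on the percent-change scale used for VAS.** Let dA and dP be the exit fractions (active, placebo), with exit unrelated to response within an arm, and let A4, A18, P4, P18 be mean percent changes at weeks 4 and 18. The bias of the carried-forward difference (active minus placebo) is dA(A4 - A18) - dP(P4 - P18). All values are assumed; negative means benefit. Exits are 10% active and 30% placebo.
- Active goes from -20 to -60, placebo flat at -20: bias = 0.10 x 40 - 0 = +4, so a true -40 becomes -36 (understated).
- Active flat at -60, placebo goes from -10 to -30: bias = 0 - 0.30 x 20 = -6, so a true -30 becomes -36 (overstated).

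**Size when the least-improved women leave.** Assumptions: 20 per arm, unit SD, correlation 0.6 between any two time points, four periods, linear improvement, exit after period 1, true difference -0.90. Placebo improves by m = 0, 0.5 or 1.0 SD.

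For an arm with final improvement M and exit fraction p, the mean carried-forward change is -(1-p)M - pM/4 + k(p). Here k(p) = (1 - 0.5) x 0.894 x phi(z_p) is the effect of selecting the least improved. The SD of change is sqrt(2 x 0.4) = 0.894, the correlation between the period-1 and period-4 changes is 0.4/0.8 = 0.5, and phi(z_p) is the standard normal density at the point cutting off p. So k(0.10) = 0.079, k(0.20) = 0.125 and k(0.40) = 0.173.

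- 30% exit in both arms: the selection terms cancel, leaving 0.7 x (-0.90) + 0.3 x (-0.225) = -0.70 for every m.
- 40% placebo, 10% active, m = 0.5: active -0.9 x 1.4 - 0.1 x 0.35 = -1.295; placebo -0.6 x 0.5 - 0.4 x 0.125 = -0.35; difference -0.945 + (0.079 - 0.173) = -1.04.

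| Exit (placebo/active) | m = 0 | m = 0.5 | m = 1.0 |
|---|---|---|---|
| 30%/30% | -0.70 | -0.70 | -0.70 |
| 40%/10% | -0.93 | -1.04 | -1.15 |
| 20%/10% | -0.88 | -0.92 | -0.95 |
| 40%/10%, no true difference | -0.09 | -0.21 | -0.32 |

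Simulation (12,000 trials per scenario) agrees to within 0.01.

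**Shape matters.** If improvement is complete by period 1, the 30%/30% result is 0.7 x (-0.90) + 0.3 x (-0.90) = -0.90, with no bias.

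**Power at 30%/30%.** Power is 87% with complete data. Under LOCF it is about 53/44/30% by t-test (m = 0/0.5/1.0) and 64/53/39% by ANCOVA. A repeated-measures model with baseline gives 78-80%. About 10 points of the gap between the t-test and the model therefore come from baseline adjustment, not from carrying forward.

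**Where the model fails.** If exit (40%/10%) depends on the unrecorded final score, the model gives -0.59 against a true -0.90, while LOCF gives -0.74 to -0.96. With equal arms both improving 1.0 SD, the model then errs by 0.31 against the drug, and rejection is 22-25%.

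**The case against.** **The endpoints are not primary, and the study is small and exploratory.** This stands. VAS and analgesic use are secondary in Protocol 10.1, and bleeding is not among the endpoints visible there. A reader might infer that the primary patient-reported BBSS result is affected too. The documents do not support that: the text where a rule would stand in Sections 13.2.2.4 and 13.2.2.5 is redacted.

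**Stage 3 values are already excluded.** This also stands. A reader might fear that scores on active drug stand in for Week 18 scores on placebo, but SAP 1 limits the first analysis to Stages 1 and 2. A woman who exits simply has missing Stage 2 data. The problem is the early value put in their place.

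**The no-change rule need not conflict with LOCF.** Read broadly, Protocol 13.2.2 would contradict the endpoint sections. The narrow reading, women with no post-baseline data at all, is more likely. Earlier protocol versions limited the efficacy population to women "who have some post-baseline efficacy data", and carrying the baseline forward gives the same zero change. Only a clarification remains.

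**The SAP may have superseded LOCF.** This cannot be excluded, since part of the SAP is not shown. But the protocol states the rule five times, and no visible SAP text replaces it.

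**The illustration is not the plan's exact analysis, and large effects need heavy early exit.** This is fair. The SD-unit figures use absolute change and a t-test, whereas VAS is analysed as percent change with a rank-test option. The percent-change cases above still show both directions. No exit rate is documented, and at 20%/10% the bias is small.

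**A model is not always better.** Correct, as the last step of the working shows. That is a reason to report two analyses under different assumptions, not to rest on LOCF alone.

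**Conclusion.** The concern holds as a matter of analysis choice, at the level of something the sponsor should change, with medium confidence. For VAS, analgesic use and bleeding, the stated rule together with the 28-day exit can put an early value into the Week 18 comparison and bias it in either direction.

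The real size is unknown. Under the stated assumptions a true -0.90 SD becomes about -0.70 at 30%/30% exit and -0.93 to -1.15 at 40%/10% (placebo/active). The error is at most about 0.05 at 20%/10%, and there is none at 30%/30% if improvement is complete by the first period. All of this rests on assumed exit rates, trajectories and correlation, and on exit driven by recorded early response.

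The documents do not show that LOCF favours the drug, nor that it accounts for the whole power gap.

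**What to change.** 1. **VAS.** Replace LOCF as the main Week 18 analysis with a likelihood-based repeated-measures model containing treatment, visit, treatment-by-visit and baseline, on all observed Stage 2 visits. Prespecify the covariance and a simpler fallback. If Visits 4 to 12 all contribute (nine visits; the schedule is not shown), an unstructured matrix has 9 x 10 / 2 = 45 parameters and may not fit with 60 women.
2. **Pill counts and bleeding days.** Use a count-appropriate or rank-based equivalent if the SAP 6.1 normality check fails; that section already provides for this ("If distributional assumptions are violated, non-parametric techniques").
3. **Sensitivity analysis.** Prespecify no change for women who exit early, and report both results. The model estimates the difference had women stayed; the other counts early exit as no benefit.
4. **Clarification only.** State in Protocol 13.2.2 that no change applies to women with no post-baseline data.

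The exit rule itself is untouched. The cost is protocol and SAP wording plus modest programming, with no new data. The downside is that the model assumes missing at random and can be more biased than LOCF if exit depends on later, unrecorded pain. Both results must therefore be shown.
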